The generation of knowledge regarding the usefulness of metformin in this specific group of patients can lay the groundwork for research on the effect of this drug in solid tumors and other pediatric neoplasms.

HYPOTHESIS

If metformin is added to standard chemotherapy during the remission induction phase in Mexican adolescents with newly diagnosed ALL, then it will decrease the level of ABCB1/MDR1 gene mRNA expression and increase AMPK expression levels, at the end of this treatment period.

OBJECTIVES

General:

- To evaluate the efficacy of metformin in modifying ABCB1 and AMPK gene expression in adolescents diagnosed with ALL during the remission induction phase.

Specific

- To describe the expression levels of ABCB1/MDR1 and AMPK genes in adolescents with ALL at diagnosis and in healthy controls.
- To compare the expression levels of ABCB1/MDR1 and AMPK genes at diagnosis and at the end of induction in adolescents with ALL treated with conventional chemotherapy and those additionally treated with metformin.
- To compare overall and disease-free survival in adolescents with ALL treated in relation to ABCB1/MDR1, and AMPK gene expression.
- To compare overall and disease-free survival in adolescents with ALL treated with conventional chemotherapy with those treated with conventional chemotherapy plus metformin.

METHODOLOGY

Type and design of study

Type of study: randomized clinical trial

Study design: analytical, experimental, longitudinal and prospective study.

Population

The population to be studied are patients with newly diagnosed ALL between 10 and 21 years.

Eligible population: patients with newly diagnosed ALL between 10 and 21 years old, diagnosed at the Hospital General de México "[name]" from February 2021 to December 2023.

Inclusion, exclusion and elimination criteria

- Inclusion criteria:
 1. Patients aged between 10 and 21 years with a new diagnosis of ALL at the Hospital General de México, [name].
 2. Patients and legally authorized person who sign the informed consent.

- Exclusion criteria:
 1. Patients with antineoplastic treatment prior to admission.
 2. Patients with Down syndrome.

- Elimination criteria:
 1. Patients who abandon treatment for more than a few weeks.4
 2. Patients who withdraw informed consent

Sample size

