To calculate the sample size, we used data from the publication by Ramos Peñafiel⁶³, where a decrease in the expression pattern of ABCB1 gene expression from high to low expression after metformin administration was 50%.

The sample size calculation was based on the formula for estimating a proportion, with a confidence level of 95% and a precision of 5%:

$$n = \frac{Z_{\alpha}^2 * p * q}{d^2}$$

A sample number of 8 patients in each group is obtained, assuming a loss of 20%, 10 patients are calculated for each group.

Definition of the variables to be evaluated and how they are to be measured

Variable	Conceptual Definition	Unit of measurement	Type of variable	Coding
Age	Time elapsed in years since birth.	Years	Quantitative	Not applicable

Gender	Male or female phenotype of the person.	Male/female	Qualitative Dichotomous	0: male 1: female
Leukocyte count at diagnosis	Number of total leukocytes reported on complete blood count at diagnosis.	X10/ml ³	Quantitative	Not applicable
Hemoglobin at diagnosis	Measurement of the amount of oxygen transport protein reported in initial complete blood count.	g/dL	Quantitative	Not applicable
Platelet count at diagnosis	Measurement of the number of platelet fragments produced by the megakaryocytes, reported in the initial complete blood count.	X10/ml ³	Quantitative	Not applicable
Immunophenotype of leukemia lymphoblastic	Cellular variant of acute lymphoblastic leukemia	B/ T	Qualitative dichotomous	0: strain B 1: lineage T
Cytogenetic alterations	Alterations in the genetic structure of leukemic cells.	None/ t(9;22)/ t(12,21)/ t(4,11), other	Qualitative polytomous	0: none 1: t(9;22), 2: t(12,21) , 3: t(4,11), 4: other
MDR-1 and AMPK gene expression.	Amplification of gene expression by RT-PCR	No expression / low expression / high expression expression	Qualitative polytomous	0: not expressed 1: high expression 2 low expression
Pre-phase response with prednisone	Decrease in total peripheral blood blast count less than 1000 after 7 days of steroid (day 0)	Present/absent	Qualitative dichotomous	0: Yes 1: No
Morphological status at day +14	Presence of blasts in bone marrow sample per day +14 referral induction	M1, M2, M3	Qualitative polytomous	0: M1 1: M2 2: M3
Morphological response at the end of induction	Presence of blasts in the bone marrow aspirate at the completion of remission induction phase.	M1, M2, M3	Qualitative polytomous	0: M1 1: M2 2: M3

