Minimal residual disease at the end of induction.	Flow cytometry measurement of the presence of 1x10 ⁻³ blasts.	Positive /Negative	Qualitative dichotomous	0: positive 1: negative
Relapse	Presence of blasts in bone marrow after remission has been achieved.	Present/absent	Qualitative dichotomous	0: absent 1: present

Time to relapse	Time from diagnosis of leukemia to relapse	Days	Quantitative	Not applicable
Death	Cessation of life	Present/absent	Qualitative dichotomous	0: absent 1: present
Time to death	Time from leukemia diagnosis to death	Days	Quantitative	Not applicable

Table 1. Variable definitions.

PROCEDURES

Patients with a newly morphological diagnosis of ALL at the Hospital General de México "[name]" will be invited to participate in this trial, and informed consent will be requested from parents and participants.

The data collection is obtained from the patients chart such as age, gender, leukocyte count, hemoglobin, platelet count and immunophenotype.

Peripheral blood samples will be collected in EDTA tube. The sample will be centrifuged obtaining mononuclear cells, and the analysis of ABCB1 and AMPK expression will be performed. This will be done on samples obtained before the start of treatment and at the end of the induction phase. Samples will be collected by peripheral vein puncture, and mononuclear cells will be separated using density gradient. Mononuclear cells are separated and suspended in PBS medium and stored at -70°C . RNA isolation is performed using TRIzol® (Invitrogen/life Technologies), and will be stored at -80°C until use. For cDNA synthesis, 2g of RNA, final volume of 20L will be combined with 200U of MMLV RT enzyme (Invitrogen, Carlsbad, CA, USA).

Expression of mRNA levels will be measured using the TaqMan gene expression assay (Applied Biosystems Foster city, CA, USA). The cut-off point between low and high expression will be determined according to mean values obtained in healthy controls, selected during case recruitment in a 2:1 ratio for each case.

Regarding treatment, patients will be randomized into 2 groups, where in both cases the conventional remission induction treatment will be given, and to intervention group metformin will be added at a dose of 1000mgm2Seday, divided into two doses, with a maximum dose of 850mg every 8 hour, orally.

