The Kolmogorov-Smirnov test will be performed for continuous variables to determine if they have normal distribution; if they have normal distribution, both groups will be analyzed by means of the t-student test; if they do not have normal distribution, the chi-square test, Fisher's exact test and Mann Whitney U test will be used for the bivariate analysis. To compare the expression of ABCB1/MDR1 and AMPK genes at the time of diagnosis and at the end of induction, McNemar's test will be used.

For the calculation of the overall and disease-free survival function, the Kaplan Meier survival test will be used for both groups and the differences between groups will be analyzed by means of the log Rank test, both for overall and disease-free survival. Similarly, the overall and disease-free survival function will be analyzed with the Kaplan Meier test and log rank for ABCB1/MDR1 and AMPK gene expression.

ETHICAL AND BIOSAFETY ASPECTS

According to the General Health Law regarding research on human subjects, this protocol is considered a higher than minimal risk research, since randomized methods of assignment to therapeutic schemes are used.

This protocol takes into account the Mexican General Health Law regarding the provision of health care services and health research, as well as national and international ethical standards.

This study will be carried out with strict observance of recognized scientific principles and respect and confidential handling of the data obtained. The security mechanisms to maintain the ethical aspects of this study are:

1. Review of this protocol by the research and ethics committees of the Hospital General de México "[name]".
2. All information obtained in this study will be made available to the Ethics and Research Committees.
3. The confidentiality of the study information is assured, as well as the identity of the patients. The identification data of the participants will be codified, assigning a consecutive participation number. The identification information and the relation between the identification numbers and the data obtained will be known only to the participating investigators and will be preserved confidentially in electronic media.
4. There will be no charge for the study, nor will there be any consistency for participation in this study. Refusal to participate in the study will not influence the patient's treatment or clinical care.

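### Survival is related to ABCB1/MDR1 and AMPK expression only through expression classes, although a quantitative TaqMan level is measured; the power lost depends on assumptions that the plan does not give

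*Combined protocol and SAP*

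**What the plan says.** The third specific objective is "To compare overall and disease-free survival in adolescents with ALL treated in relation to ABCB1/MDR1, and AMPK gene expression". Under Procedures, "Expression of mRNA levels will be measured using the TaqMan gene expression assay", which yields a quantity. The same paragraph then turns it into classes: "The cut-off point between low and high expression will be determined according to mean values obtained in healthy controls". Table 1 carries the variable forward only as qualitative, coded "0: not expressed 1: high expression 2 low expression".

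The one analysis planned for this objective is in the statistical analysis section: "the overall and disease-free survival function will be analyzed with the Kaplan Meier test and log rank for ABCB1/MDR1 and AMPK gene expression". No Cox model, trend test or hazard ratio appears anywhere in the plan.

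On sampling, "This will be done on samples obtained before the start of treatment and at the end of the induction phase". The statistical section does not say which of the two samples is to be related to survival. On size, "A sample number of 8 patients in each group is obtained, assuming a loss of 20%, 10 patients are calculated for each group". Follow-up is 12 months from the start of treatment.

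**The concern.** Kaplan-Meier curves and the log-rank test compare groups. Two patients in the same class count as identical however far apart their mRNA levels are, and two patients just either side of the healthy-control mean count as different. With 16 to 20 patients and one year of follow-up there will be few events, so little information can be spared. If risk rises or falls gradually with expression, the planned test will miss the relation more often than a test on the level would. The log-rank result also comes without an estimate of the size of the relation. A non-significant result would then leave the reader unable to judge what has been excluded.

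The point concerns expression as a predictor of survival. It does not concern the comparison of expression between arms or between time points.

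**Working it through.** **The plan's own figures.** No power, event count, hazard ratio or class split is given for this objective, so there is no planned figure to reproduce. The only design figure is the sample size. Its loss step reproduces: 8/0.8 = 10 per group, hence 16 evaluable and 20 enrolled. The 8 itself does not follow from the stated formula: 1.96² × 0.5 × 0.5 / 0.05² ≈ 384. That is a separate matter, and 16 to 20 patients is taken as given here.

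**Deaths to expect.** The problem statement puts 5-year overall survival at around 50%. Under a constant hazard (an assumption), 12-month mortality is 1 − 0.5^(1/5) = 0.129. That is 20 × 0.129 = 2.6 deaths, or 16 × 0.129 = 2.1. The plan says that adolescents fare worse, so the number could be higher.

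**Approximate formula.** With E events and hazard ratio HR per SD, power ≈ Φ(√E · |log HR| · r − 1.96). Here r = 1 for the level, and r = φ(c)/√(p(1−p)) for a cut at c that puts a share p in the high class.
- E = 8, HR 1.5, p = 0.5: r = 0.798 and √8 × 0.405 = 1.147. Level Φ(−0.813) = 20.8%; cut Φ(0.915 − 1.96) = 14.8%. Loss 6.0 points.
- E = 10, HR 2, p = 0.2: r = 0.700 and √10 × 0.693 = 2.192. Level Φ(0.232) = 59.2%; cut Φ(1.534 − 1.96) = 33.5%. Loss 25.7 points.

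**Simulation.** The formula is rough at these numbers, so both tests were simulated. Assumed: 20 patients, 12 months, log expression normal, hazard log-linear in expression, two-sided 5%. Null martingale residuals were multiplied by the high/low indicator (log-rank score) or by log expression (Cox score), with 999 permutations and 1,500 trials per cell. Event-free refers to 12 months at mean expression.

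| Event-free | HR per SD | Share high | Cut, % | Level, % | Gain, points |
|---|---|---|---|---|---|
| 70% | 2 | 50 / 30 / 20% | 21.9 / 29.2 / 28.5 | 36.2 / 35.5 / 35.3 | 14.3 / 6.3 / 6.8 |
| 70% | 3 | 50 / 30 / 20% | 44.3 / 56.6 / 51.4 | 70.7 / 72.1 / 68.2 | 26.4 / 15.5 / 16.8 |
| 50% | 2 | 50 / 30 / 20% | 31.8 / 33.9 / 30.5 | 47.9 / 51.3 / 47.5 | 16.1 / 17.4 / 17.0 |
| 50% | 3 | 50 / 30 / 20% | 61.1 / 62.9 / 56.2 | 82.4 / 83.9 / 81.5 | 21.3 / 21.0 / 25.3 |

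With no effect, both tests rejected in 3–5%. The Monte Carlo standard error of each power is at most √(0.25/1500) = 1.3 points. Rounded outward, the gains are about 6–18 points at HR 2 and 16–27 at HR 3.

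**How far this moves with the inputs.**
- HR 1.5 per SD (70–87% event-free, 20–50% high): gain 2–9 points, with the level's own power only 8–16%.
- 70–80% of patients high, HR 2 or 3: gain 24–61 points.
- 16 patients, 30–50% high, HR 2 or 3: gain 5–26 points.
- Large-sample score tests in place of permutation (20 patients, overall event rate 30–50%, 20–50% high): gain 3.0–16.7 points at HR 2 and 8.0–23.6 at HR 3. Over a wider grid (event rate 20–50%, HR 1.5–3, 20–80% high) the gain runs from −3 to +65.
- True jump at the cut, HR 4: the cut wins by 15–22 points (50–70% against 34–50%).
- About 13% deaths, HR 2 per SD: 19–21% for the level and 4–15% for the cut.

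**Limits of the check.** Two classes were simulated, whereas Table 1 has three. A three-group log-rank test also ignores differences within a class and, in its general form, the order of the classes. The table is not stratified by arm. Stratified runs at 70% event-free gave the level 34% at HR 2 and 67% at HR 3, with a similar gain.

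**The case against.** The cut comes from an external source, the mean of healthy controls, and its source is fixed in advance. It is therefore not tuned to outcome, and it matches the high-to-low change on which the sample size is based. This stands: the cut carries no bias from data-driven selection, and it has a natural reading.

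The documents also give no more support for a log-linear hazard than for a threshold, and under a threshold at the healthy mean the planned test is the better one. This stands as well. It is the main reason to state the gain as conditional and to keep the class display.

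The number of events limits this objective more than the cut does. At a hazard ratio of 2 per SD the level still misses 49–65% of true associations (100 minus 51.3 and 35.3, rounded). A reader might infer that a null result would be due only to the cut; these figures do not support that. They do argue for reporting an estimate with an interval, which the log-rank plan does not provide.

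A reader might also infer that a usable level exists for every patient. Table 1 foresees a not-expressed class, and patients who die or leave before the end of induction will have no second sample.

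**Conclusion.** The point holds. A quantitative level is measured, only classes enter the survival analysis, and nothing else is planned for the third objective. With a log-linear hazard, 20 patients, 50–70% event-free and 20–50% classed high, the level gains about 6–18 points of power at a hazard ratio of 2 per SD and about 16–27 at 3 per SD.

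It is tempting to read 6 to 27 points as a fixed loss built into this plan. The documents do not support that. They give no hazard ratio, 12-month event rate or class split. The gain is a few points at 1.5 per SD, larger if most patients are high, and reversed under a true threshold at the cut.

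Nor does the level make the objective well powered: about 35–51% at a hazard ratio of 2 per SD. With some 2 to 3 deaths expected under the constant-hazard assumption, overall survival may be uninformative either way. The change is worth making because it uses data already collected and replaces a bare test with an estimate. The results should still be presented as exploratory.

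**What to change.** In the statistical analysis section:

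- Analyse overall and disease-free survival against the log-transformed pre-treatment TaqMan level with a Cox model, one gene at a time, stratified by arm, with a permutation p-value (permuting within arm). Report the hazard ratio per SD or per doubling with its 95% interval.
- State that the pre-treatment sample is used, since the plan leaves this open. If the end-of-induction level is also analysed, start the survival clock at that sample (a landmark analysis).
- Assign samples with undetectable expression a stated lowest value.
- Keep the Kaplan-Meier curves by expression class as a descriptive display.

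The cost is a few lines of text, with no new samples, assays or patients. The permutation step may need a short program outside the named package. The statistical price is an assumed monotone relation, and a loss of power if there is a true threshold at the healthy-control mean.

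### Survival by gene-expression class is tested with an ordinary log-rank test in about 20 patients; if a class holds one or two patients, the false-positive rate usually exceeds the nominal 5%

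*Combined protocol and SAP*

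**What the plan says.** - **Test.** One specific objective relates overall and disease-free survival to ABCB1/MDR1 and AMPK expression. Under Statistical Analysis both outcomes "will be analyzed with the Kaplan Meier test and log rank for ABCB1/MDR1 and AMPK gene expression". SPSS 25.0 is the named software. No exact or permutation version is mentioned for survival; Fisher's exact test appears only for the bivariate comparisons.
- **Classes.** Table 1 lists the levels as "No expression / low expression / high expression expression", coded "0: not expressed 1: high expression 2 low expression". Under Procedures, "The cut-off point between low and high expression will be determined according to mean values obtained in healthy controls". There is no minimum class size and no merging rule. The plan does not say whether expression at diagnosis or at the end of induction defines the survival classes.
- **Numbers.** Under Sample size: "A sample number of 8 patients in each group is obtained, assuming a loss of 20%, 10 patients are calculated for each group". Follow-up is 12 months. No 12-month event rate is given.

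**The concern.** The log-rank p-value comes from a chi-square approximation to the null distribution. That approximation is poor when one group is very small. Randomisation in blocks keeps the arms near 10 v 10, but nothing does this for expression classes. A cut-off set in healthy people and applied to patients with leukaemia gives no reason to expect balanced classes.

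This is a question of error rate, separate from low power. The trial could report expression as prognostic on the strength of one patient's early event. There are at least four such tests (two genes by two outcomes) and no multiplicity rule.

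**Working it through.** **The plan's own figure.** The documents state no error rate or power for this test, so the only figure to reproduce is the sample size. The stated formula with p = 0.5 ("after metformin administration was 50"%) and "with a confidence level of 95% and a precision of 5"% gives 1.96² × 0.5 × 0.5 / 0.05² = 384.2, so 385, not 8. The loss step does reproduce: 8 / 0.8 = 10. The gap between 385 and 8 is a separate matter. Only the planned total of 20 (16 after loss) is used below.

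**Inputs.** From the documents: 20 patients, two or three classes, censoring at 12 months, ordinary log-rank test. Assumed: the class sizes, 12-month event-free proportions of 50, 70 and 85%, exponential event times and no true difference.

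**A class of one among 20, by hand.** Suppose the lone patient has the r-th event. Then E = Σ 1/(20−i) and V = Σ [1/(20−i)][1 − 1/(20−i)] for i = 0 to r−1, and the statistic is (1−E)²/V.

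- r = 1: 0.95² / 0.0475 = 19.0, p ≈ 0.00001. Under the null this patient is first with probability 1/20, so the exact p is 0.05.
- r = 2: 8.27, p ≈ 0.004.
- r = 3: 4.73, p ≈ 0.03.
- r = 4: 2.99, not significant. Later positions do not reach 3.84 either; the last gives 3.37.

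The test therefore rejects when the lone patient is among the first three events. With M events in total, the false-positive rate is E[min(M, 3)]/20 = [3 − 3P(M=0) − 2P(M=1) − P(M=2)]/20, with M binomial on 20 patients:

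- 50% event-free: 3.00/20 = 15.0%.
- 70%: (3 − 3×0.0008 − 2×0.0068 − 0.0278)/20 = 14.8%.
- 85%: (3 − 3×0.0388 − 2×0.1368 − 0.2293)/20 = 11.9%.

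**Other class sizes, by simulation** (null rejection rate in %; standard error about 0.3 points near 5% and 0.5 near 20% with 6,000 trials per cell; the 15 v 5 row is a separate check):

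| Classes | 50% event-free | 70% | 85% |
|---|---|---|---|
| 10 v 10 | 4.9 | 4.5 | 2.4 |
| 15 v 5 | 5.5 | 4.3 | 2.7 |
| 18 v 2 | 9.1 | 6.8 | 5.3 |
| 14/4/2 | 9.6 | 7.6 | 6.4 |
| 15/4/1 | 14.9 | 13.7 | 11.0 |
| 17/2/1 | 17.9 | 15.2 | 12.5 |
| 18/1/1 | 20.9 | 20.1 | 17.4 |

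A wider scan took 13 splits of 20 with a class of one or two, at event rates from 10 to 70% and 20,000 trials per cell. It gave 3.6 to 21.7%, with 112 of 117 cells above 5%. The five exceptions were 2/8/10 and 2/9/9 at event rates of 20% or less. With 16 patients the range was 4.8 to 24.9%. Over the same event rates, 6/7/7 reached at most 7.2% and 10 v 10 at most 5.6%.

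**How often would a class be that small?** With two classes and a 10% share (assumption), the chance of one or two in 20 is 20(0.1)(0.9)¹⁹ + 190(0.1)²(0.9)¹⁸ = 0.270 + 0.285, about 55%. With a 20% share it is about 19%, and with 30% about 3%. With three classes, one of them at 5 to 10%, it is about 55 to 65%; with equal thirds, about 5%.

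**The alternative test.** A permutation log-rank test was run on null data with 20 patients, for seven splits with a class of one or two and event rates of 20, 30 and 50%. It rejected in 1.4 to 5.4% of trials; the chi-square version rejected in 4.0 to 21.8% of the same trials.

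**The case against.** Several objections have force.

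- **The inflation depends on class sizes that the documents do not give.** This stands. With classes of about five or more there is little to correct.
- **The analysis may use two classes.** Only one cut-off is defined, there is no rule for non-expression, and McNemar's test, planned for the change in expression, takes a binary variable. If so, the three-class figures fall away, but 18 v 2 and 19 v 1 remain.
- **The objective is secondary.** The hypothesis and sample size concern change in expression, and no decision rule is attached to these curves. This limits the weight of the point.

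Two stronger readings are tempting but not supported.

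- **A reader might infer that one early death in any tiny class gives p < 0.05.** For 18 v 2, put the first death in the class of two, let its other member survive, and place later deaths in the large class. Then p is 0.023 with 2 events in total, 0.071 with 3, 0.32 with 6 and 0.73 with 10. The assumed event-free proportions imply about 3, 6 and 10 events.
- **A reader might infer that a false prognostic claim is likely.** All four tests were simulated together, taking the genes as independent and half of disease-free-survival events as deaths (assumptions). The chance of any p < 0.05 was 22/16/15% for 18 v 2, and 47/43/35% with 18/1/1 for both genes, at 50/70/85% event-free. No simulated scenario reached one half. Balanced 10 v 10 classes already gave 15/13/6%, so part of this is multiplicity.

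**Conclusion.** The point holds conditionally. If an expression class holds one or two of about 20 patients, the planned test usually exceeds its nominal 5%: about 5 to 10% for 18 v 2, 12 to 15% for 19 v 1 and up to about 21% for 18/1/1, at assumed event-free proportions of 50 to 85%. A false prognostic finding is then materially more likely than 5% per test, most clearly with a class of one. It is not shown to be likely overall. The comparison of randomised arms is not affected at 10 v 10. Confidence is moderate: the arithmetic is firm, but the class sizes are unknown.

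**What to change.** Add one sentence to Statistical Analysis: p-values for overall and disease-free survival by ABCB1/MDR1 and AMPK class come from an exact or Monte Carlo permutation log-rank test, whatever the class sizes. Keep the ordinary log-rank test for the comparison of arms.

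Merging non-expression with low expression is optional and should be fixed in advance if used. It does not replace the permutation test: it does nothing when the high class is the small one, or when the merged class is still small.

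The cost is a few lines of code, possibly outside SPSS, with no new patients or data. Some p-values will be less favourable; in a 19 v 1 split a first event in the lone patient gives p = 0.05 at best. The change does not address multiplicity across the four tests.
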